8.1 Screening

The following procedures and tests are to be performed within **28** days (unless otherwise specified) of study enrollment to confirm eligibility. Baseline and Cycle 1 Day 1 procedures may be completed on the same day, however, screening assessments to confirm eligibility **MUST** have already been determined. Refer to Table 4 for details.

1. Informed consent
2. Review of past medical history and previous therapies for NSCLC
3. Eligibility criteria review (Inclusion/exclusion)
4. Demography/Baseline characteristics, smoking history
5. A directed physical examination will be performed at the visit with vital signs including pulse, blood pressure, temperature, oxygen saturation, weight
6. Height
7. ECOG Performance status
8. Routine blood work (CBC, chemistries)
9. EKG in triplicate
10. Echocardiogram/Muga to assess LVEF
11. Pregnancy test if applicable
12. Tumor Histology
13. EGFR mutation status
14. Review of baseline sign/symptoms
15. Review of concomitant medications
16. Staging Disease assessment: Brain MRI, CT scan of chest and abdomen

8.2 On-Study Treatment Period: Day 1 of each cycle or as noted in Table 4

1. Review of interval medical history, concomitant medications and assessment of performance status
2. A directed physical examination will be performed at the visit with vital signs including pulse, blood pressure, temperature, oxygen saturation, weight
3. Laboratory: chemistry, and hematology
4. A repeat ECG may be performed at the discretion of the investigator or per institutional standard.
5. Echocardiogram/MUGA will be repeated if clinically indicated based on assessment of the investigator or per institutional standard
6. MRI of the brain to be performed with every 3 cycles starting with cycle 4 (cycles 4, 7, 10, 13 etc...) in patients with known brain metastases to assess for intracranial disease progression. Patients without brain metastases will undergo repeat brain imaging as clinically indicated.
7. Adverse event assessment
8. Review of study drug and diary
9. Pregnancy test (if applicable)

10. CT Chest/abdomen are done on day 1 of cycle 3, and then on cycles 5, 7, 9, 11, and 13 (every 2 cycles for the first year of study therapy). Then every 3 cycles (i.e. 16, 19, 22).

8.3 End of Study Treatment (30 days (+/- 3 days) after study therapy stops)

1. Review of interval medical history since the last visit and assessment of performance status
2. A directed physical examination will be performed at the visit with vital signs including pulse, blood pressure, temperature, oxygen saturation, weight
3. Laboratory: chemistry and hematology

8.4 Follow-up Period

1. After discontinuing study therapy patients will be followed for overall survival every 3 months by telephone or review of medical records until death or a maximum of 2 years. **Subsequent therapy and survival status will be documented.** If molecular testing performed (e.g. molecular testing of tumor biopsy or circulating tumor DNA) the results of the testing will be recorded if available. Patients who discontinue therapy for reasons other than disease progression will be followed for disease progression. The imaging schedule is at the discretion of the treating physician, but the recommended interval is every 6 to 12 weeks.

8.5 End of Study

The end of study will be defined as the time at which all patients have discontinued study therapy and study report is accepted for publication.

8.6 Study Assessments

8.6.1 Medical History

The history will be reviewed, with the patient, using the health care provider notes (i.e. the investigator's and/or designees note).

8.6.2 Physical Exam

A directed physical examination will be performed at the visits as indicated in the time and events table. Performance status will be assessed at screening, prior to the first dose of study treatment, at the beginning of each cycle, and at discontinuation according to ECOG criteria as discussed in Appendix 1.

9.0 INVESTIGATIONAL THERAPY

9.1 Study Therapy

AstraZeneca will supply osimertinib tablets for oral administration as a single daily dose of 80 mg. Tablets can be taken whole with approximately 240 ml water, with or without regard to food. Study drugs will be taken by patients at home after they have received administration instructions. Doses should be taken approximately 24 hours apart at the same time-point each day.

Doses should not be missed. If a patient misses taking a scheduled dose, within a window of 12 hours, it is acceptable to take the dose. If it is more than 12 hours after the dose time, the missed dose should not be taken and patients should be instructed to take the next dose at the next scheduled time. If a patient vomits after taking osimertinib, they should not make up for this dose, but should take the next scheduled dose. The missed doses and reason should be recorded in the patient diary.

A study cycle is defined as 28 consecutive days and patients will take their study drug on days 1-28 of each cycle. Study drug may be interrupted up to 21 days. Additional information about the investigational product may be found in the IB for each agent.

Investigational product	Dosage form and strength	Manufacturer
Osimertinib	40 mg tablet	AstraZeneca
Osimertinib	80 mg tablet	AstraZeneca

Reported adverse events and potential risks are described in Section 2. No investigational or commercial agents or therapies other than those described in this study may be administered with the intent to treat the patient's malignancy. All patients will be requested to maintain a medication diary of each dose of medication. The medication diary will be returned to clinic staff at the end of each cycle.

9.1.1 Dose Modification

Dose delays and modifications will be made as indicated below. The descriptions and grading scales found in the revised NCI Common Terminology Criteria for Adverse Events (CTCAE) version 4.03 will be utilized for dose delays and dose modifications. A copy of the CTCAE version 4.03 can be downloaded from the CTEP website:

http://ctep.cancer.gov/protocolDevelopment/electronic_applications/ctc.htm.

1. If any patient experiences a CTCAE grade 3 or intolerable grade 2 adverse event related to osimertinib, dosing will be interrupted and supportive therapy administered as per institutional standard. Patients will not be permitted to restart osimertinib until toxicities have resolved to CTCAE grade ≤ 1 .
2. If grade 3 or intolerable adverse event does not resolve with 21 days, patient should permanently discontinue study therapy
3. If first grade 3 or intolerable grade 2 adverse event which resolves within 21 days patient may restart at 80 mg dose level or 40 mg dose delay (at the discretion of the treating physician)
4. If second grade 3 or intolerable grade 2 adverse event which resolves within 21 days patient must have dose reduced to 40 mg daily
5. If patient is on 40 mg dose level and experiences a grade 3 or intolerable grade 2 adverse event patient must discontinue study therapy
6. Patients experiencing corneal ulceration (any grade), interstitial lung disease (ILD), and QT_c interval prolongation with signs/symptoms of serious arrhythmia will permanently discontinue the osimertinib.
7. For patients with grade 3 QT_c prolongation dose reduction to 40 mg daily is mandatory

Patients who are unable to remain on study therapy because of toxicity should be considered for treatment, as per institutional standard.

Dose reduction schema for grade 3 or intolerable grade 2 adverse events.

For specific management other than pulmonary, QT_c prolongation, and corneal ulceration or grade 3 ophthalmologic adverse events please refer to table and text

[figure not shown]

TABLE 2: DOSE REDUCTION

Dose level	Osimertinib dose	Schedule
“0”	80 mg	Daily
“-1”	40 mg	Daily

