2.4 Clinical safety and Rationale for Dose Selection, Regimen, and Treatment Duration

Osimertinib 80 mg PO once-daily dose, approved by the FDA, has an acceptable safety profile for the intended advanced NSCLC population. The standard clinical practice is to continue targeted therapies until disease progression or unacceptable toxicity.

In the AURA3 study:

The overall incidence of all causality AEs was 97.8% for the osimertinib arm and 99.3% for the chemotherapy arm. Regardless of causality, the majority of all adverse events (AEs) reported with osimertinib were mild or moderate in severity. Adverse events of Common Terminology Criteria for Adverse Events (CTCAE) Grade ≥ 3 were reported for a lower proportion of patients in the osimertinib arm than in the chemotherapy arm: 63 (22.6%) vs. 64 (47.1%) patients, with 16 (5.7%) and 46 (33.8%) of CTCAE Grade ≥ 3 considered related treatment by the investigator for osimertinib and chemotherapy respectively. A number of serious adverse events (SAEs) were reported for patients in the osimertinib arm than the chemotherapy arm: 50 [17.9%] vs. 35 [25.7%] patients. SAEs considered to be possibly related to study drug were less common in the osimertinib arm (8 [2.9%] patients) than the chemotherapy arm (17 [12.5%] patients)

During the treatment period or 28-day follow-up period, death was due to disease under investigation plus a fatal AE in 0.7% of patients in each treatment arm; death due to a fatal AE only occurred in 0.7% osimertinib vs. no chemotherapy patients. All other deaths were due to disease under investigation only.

Osimertinib is well tolerated. Adverse events leading to discontinuation (6.8% osimertinib arm vs 10.3% chemotherapy arm), dose reduction (2.9% osimertinib arm vs 12.5% pemetrexed, 28.6% cisplatin, 10.6% carboplatin of the chemotherapy arm), or dose interruption/delay (12.9% osimertinib arm vs 20.6% pemetrexed, 11.9% cisplatin, and 16.0% carboplatin) were low and less common in the osimertinib arm than in the chemotherapy arm.

The most commonly reported AEs (ie, $>15\%$) in the osimertinib arm vs the chemotherapy arm, respectively were: diarrhea (40.5% vs. 11.0%), rash ([grouped terms] 33.7% vs. 5.9%), dry skin (18.6% vs. 4.4%), decreased appetite (17.9% vs. 36.0%), paronychia (16.5% vs. 1.5%), cough (16.5% vs. 14.0%), nausea (16.1% vs. 49.3%), and fatigue (15.8% vs. 27.9%).

In the osimertinib clinical program:

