9.1.2 Management of adverse effects

Symptom-specific toxicity management

Guidance for toxicity management will be as indicated below for patients enrolled, and investigators should manage toxicities per institutional standards and the specific clinical circumstances. Other toxicities should be managed as per institutional standards or at the discretion of the investigator.

For additional details, please refer to the table and text below:

TABLE 3 DOSE MODIFICATION GUIDELINES

NCI-CTCAE (v4.03) Grade	Dose Modification	Guideline for Management
Diarrhea		
Grade 1	None	Consider loperamide (4 mg at first onset, followed by 2 mg q2-4 hours until free of diarrhea for 12 hours, maximum daily dose of 16 mg/day).
Grade 2	None	Loperamide (4 mg at first onset, followed by 2 mg every 2-4 hours until free of diarrhea for 12 hours, maximum daily dose of 16 mg/day).
Grade 3 or intolerable grade 2	Hold study treatment for up to 21 days	Dose modification as noted, with supportive care per PI discretion.
Grade 4	Discontinue study treatment.	Supportive care as per intuitional standard
Rash		
Grade 1 and 2 tolerable rash	None	Any of the following, at the discretion of the investigator: 
 1. Oral antibiotics (tetracycline, minocycline, doxycycline) 2. Topical clindamycin, diphenhydramine, topical corticosteroids or emollient cream
Grade 2 intolerable or grade 3 rash	Study treatment interruption for up to 21 days	Manage as described above with both oral antibiotics and topical agent. Oral corticosteroids may be considered at the discretion of the investigator.
Grade 4	Discontinue study treatment	Manage as described above with both oral antibiotics and topical agent. Oral corticosteroids may be considered at the discretion of the investigator.
Paronychia		
Grade 1	None	Topical antibiotic bid and vinegar soaks (soaking finger or toes in a 1:1 solution of white vinegar in water for 15 minutes every day)
Grade 2	May continue at current dose or dose reduce at the discretion investigator	Topical antibiotic BID and vinegar soaks as outline above Topical silver nitrate weekly

39

The information contained in this document is regarded as confidential, and may not be disclosed to another party unless such disclosure is required to initiate the study, to conduct study-related activities, or to comply with national, state, or local laws and regulations. Written authorization from the coordinating site and sponsor is required for disclosure otherwise.

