Grade 2 intolerable or grade 3	Study treatment interruption for up to 21 days	Topical antibiotic bid and vinegar soaks as outline above Topical silver nitrate weekly Consider nail avulsion or removal
Grade 4	Discontinue study treatment	
Hepatic Transaminases and/or total bilirubin: please refer criteria for Hy's law provided in appendix 3		
Grade 1	None	Observation
Grade 2	None	Observation
Grade 3	Study treatment interruption for up to 21 days	Observation until laboratory values return to Grade 1
Grade 4	Discontinue study treatment	
Pulmonary Events if possibly Interstitial Lung Disease (ILD)		
All Grades	Temporarily interrupt study treatment pending the diagnostic evaluation. If the pulmonary adverse event is felt to be related to osimertinib, then permanently discontinue osimertinib.	Unexplained dyspnea, either new or progressive, should be thoroughly evaluated. Where ILD is suspected, administer corticosteroids at a dose of 1 to 2 mg/kg/day prednisone equivalents for Grade 2 or greater pneumonitis, followed by corticosteroid taper.
Cardiac		
Grade 3	QTc interval greater than 500 msec on at least 2 separate ECGs	Withhold osimertinib until QTc interval is less than 481 msec or recovery to baseline if baseline QTc is greater than or equal to 481 msec, then restart at a reduced dose (40 mg)
Grade 4	QTc interval greater than 500 msec or > 60 msecs from baseline and with signs/symptoms of serious arrhythmia	Permanently discontinue osimertinib
Management of elevated creatine kinase: please check for drug-drug interactions and refer to appendix 2 for potential drug-drug interactions		
Grade 1	None	Observation (assess for drug-drug interactions contributing to elevation. Please refer to appendix 2)
Grade 2	None	Observation (assess for drug-drug interactions contributing to elevation. Please refer to appendix 2)

40

The information contained in this document is regarded as confidential, and may not be disclosed to another party unless such disclosure is required to initiate the study, to conduct study-related activities, or to comply with national, state, or local laws and regulations. Written authorization from the coordinating site and sponsor is required for disclosure otherwise.

Grade 3	Study treatment interruption for up to 21 days	Observation until laboratory values return to Grade 1 (assess for drug-drug interactions contributing to elevation. Please refer to appendix 2)
Grade 4	Discontinue study treatment	Discontinue study treatment
Ocular		

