	Corneal ulceration	Permanently discontinue osimertinib
Grade > 3 or eye symptoms that are clinically significant and/or persistent (>7 days)	Referral to ophthalmologist	Permanently discontinue osimertinib
Grade 4	Referral to ophthalmologist	Permanently discontinue osimertinib
Other		
Grade ≥ 3 adverse event	If Grade 3 or higher adverse reaction improves to grade ≤ 1 after withholding of osimertinib for up to 21 days	Osimertinib may be restarted at the same dose (80 mg) or a lower dose (40 mg) at the discretion of the investigator
	If grade 3 or higher adverse reaction that does not improve to grade ≤ 1 after withholding for up to 21 days.	Permanently discontinue osimertinib

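### For a second, resolving grade 3 reaction of an unlisted type on 80 mg, section 9.1.1 requires 40 mg but the Other row of Table 3 still permits 80 mg

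*Combined protocol and SAP*

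**What the plan says.** Section 9.1.1 (Dose Modification) gives a numbered sequence for osimertinib-related grade 3 or intolerable grade 2 events. Item 3 deals with the first: "If first grade 3 or intolerable grade 2 adverse event which resolves within 21 days patient may restart at 80 mg dose level", with 40 mg as the alternative, at the treating physician's discretion. Item 4 deals with the next: "If second grade 3 or intolerable grade 2 adverse event which resolves within 21 days patient must have dose reduced to 40 mg daily". Item 5 requires discontinuation if such an event occurs on 40 mg. The section later refers the reader onward for management of events other than pulmonary events, QTc prolongation and "corneal ulceration or grade 3 ophthalmologic adverse events please refer to table and text".

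Section 9.1.2 (Management of adverse effects) introduces Table 3 with "Guidance for toxicity management will be as indicated below for patients enrolled". It leaves toxicities that it does not describe to institutional standards or the investigator's discretion. The last row of Table 3, labelled Other, applies to grade 3 or higher events. Its condition begins "If Grade 3 or higher adverse reaction improves to grade" and goes on to specify grade 1 or less after a hold of up to 21 days. The action is: "Osimertinib may be restarted at the same dose (80 mg) or a lower dose (40 mg) at the discretion of the investigator". The row does not mention first or second events and does not refer back to section 9.1.1.

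**The concern.** The Other row repeats the choice in item 3 but drops the word that confines it to a first event. Read as printed, it lets an investigator return a patient to full dose after a second grade 3 reaction, which item 4 forbids. The case is foreseeable: item 3 allows restart at 80 mg after a first event, so some patients can have their second event on 80 mg, and item 4 is written for them.

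What is at stake is patient safety and equal handling across sites. The protocol provides for outside sites, and two of them could dose the same patient differently, each citing the protocol. A site that relied on the row could also commit a deviation from item 4 without knowing it.

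**Working it through.** The plan states no figure on this point, so the check is mainly a comparison of texts. Take a patient on 80 mg with a related grade 3 reaction of a type not named in Table 3, improving to grade 1 or less within 21 days.

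| Situation | Section 9.1.1 | Table 3, Other row |
|---|---|---|
| First event on 80 mg | 80 mg or 40 mg (item 3) | 80 mg or 40 mg |
| Second event on 80 mg | 40 mg only (item 4) | 80 mg or 40 mg |
| Event on 40 mg | Discontinue (item 5) | Not addressed: the row's same dose is 80 mg |

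The rules differ only in the second line.

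**Boundaries of the conflict**

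- Intolerable grade 2 events are not in the Other row.
- The diarrhea, rash, paronychia, hepatic and creatine kinase rows set a hold but no restart dose, so items 3 to 5 complete them without contradiction.
- Grade 3 QTc prolongation leads to 40 mg in both places.
- Items 3 to 5 name grade 3 and intolerable grade 2 only, whereas the Other row covers grade 3 or higher. A second unlisted grade 4 reaction is therefore not a conflict with item 4. It falls only under the row, and any repair has to cover it.

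**Size**

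The documents give no rate of repeat events. Two AURA3 figures in section 2.4 serve as rough benchmarks, on the assumption that AURA3 rates carry over to this population.

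1. Related events of grade 3 or higher. Section 2.4 gives "with 16 (5.7%) and 46 (33.8%) of CTCAE Grade" 3 or higher, osimertinib arm first. The arm size follows from 63 patients being 22.6%: 63 / 0.226 = about 279. Then 16 / 279 = 5.7% (exact 95% CI 3.3% to 9.1%), and 37 × 0.0573 = 2.1 patients (1.2 to 3.4). An affected patient must have at least one such event, so this is a ceiling. It also counts first events, listed toxicities, grade 4 and higher events, and events that do not resolve.
2. Dose reductions for adverse events, 2.9% of the osimertinib arm: 37 × 0.029 = 1.07 patients. This counts reductions for any adverse event. AURA3's reduction rules are not given, so it is a benchmark and not a bound.

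The conflict needs a second event that is grade 3, unlisted and resolving, in a patient still on 80 mg. That is a small part of either count.

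**The case against.** The strongest reply is that the texts can be harmonised. Item 4 says must and the row says may, so giving 40 mg satisfies both and no site is forced to break one rule to keep the other. Section 9.1.1 is written as a directive, while section 9.1.2 calls itself guidance and offers Table 3 for further detail. Most rows of the table make sense only when read with items 3 to 5, so the protocol already expects the two to be used together. This is a sensible reading, and it is why the severity is low. It does not remove the problem, because the row names 80 mg as a permitted dose, no visible sentence gives item 4 precedence, and section 9.1.2 itself leaves undescribed toxicities to discretion.

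A reader might infer that section 9.1.1 sends sites to this very row and so puts it above item 4. The text does not support that. The referral names no table number and no row, and it stands under the heading of the dose-reduction schema, beside a figure that is not shown; it may be a note to that figure. The figure may well display the event sequence and so make a mistake less likely, but it cannot change the wording of the row.

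It is also fair that the clinical consequence is limited. Both rules require the drug to be held, recovery to grade 1 or less, and recovery within 21 days, and the dose in dispute is the approved one.

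**Conclusion.** The row is wrong as written, with low severity. It leaves two operative dosing rules for one narrow case: a second, related, unlisted grade 3 reaction that resolves in time in a patient still on 80 mg. The expected number affected is well under one of 37. That is a judgement from the two AURA3 benchmarks, and it assumes that those rates apply here. A numeric range would need a repeat-event rate, which the documents do not supply.

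Two stronger inferences should be resisted. One is that dose reduction in the plan is inconsistent in general; the comparison above shows one cell of one row. The other is that the conflict could bias the efficacy results. With so few patients concerned there is no basis for that, and section 2.3 reports no apparent relationship between osimertinib exposure and response rate, duration of response or PFS over 20 to 240 mg. The same section does report more rash, diarrhea and interstitial lung disease with higher exposure, which is why the point belongs under safety.

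**What to change.** Reword the Other row of Table 3 in two steps.

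1. Limit the choice of 80 mg or 40 mg to a first event in a patient on 80 mg.
2. Add: for a second grade 3 or higher event on 80 mg that improves to grade 1 or less within 21 days, restart only at 40 mg; for a grade 3 or higher event on 40 mg, discontinue (9.1.1 items 4 and 5).

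Saying grade 3 or higher matters. A bare cross-reference to items 4 and 5 would leave a second unlisted grade 4 reaction without a rule.

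Do not add a general statement that section 9.1.1 overrides Table 3, because the table is stricter in places. The pulmonary row, for example, says "If the pulmonary adverse event is felt to be related to osimertinib, then permanently discontinue osimertinib". The ocular, pulmonary and QTc rules and the grade 4 rules for named toxicities should stay as they are.

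The cost is a wording amendment to one row, with the usual IRB approval. It needs no extra patients, visits or procedures and no change to the statistical design.

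### The 9.1.1 dose ladder and the Table 3 Other row give conflicting restart and stop rules for second events and for events on 40 mg, and the ladder never names grade 4

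*Combined protocol and SAP*

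**What the plan says.** Section 9.1.1 sets out a ladder. Item 1 is the trigger: "If any patient experiences a CTCAE grade 3 or intolerable grade 2 adverse event related to osimertinib, dosing will be interrupted". Item 2 deals with non-resolution: "If grade 3 or intolerable adverse event does not resolve with 21 days, patient should permanently discontinue study therapy". Item 3 leaves the dose after a first resolved event to the physician, at 80 mg or 40 mg. Item 4 is mandatory: "If second grade 3 or intolerable grade 2 adverse event which resolves within 21 days patient must have dose reduced to 40 mg daily". Item 5 is also mandatory: "If patient is on 40 mg dose level and experiences a grade 3 or intolerable grade 2 adverse event patient must discontinue study therapy". None of these five items names grade 4, and the title of the accompanying schema has the same limit. Items 6 and 7 concern only corneal ulceration, interstitial lung disease and QTc prolongation.

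Table 3 in section 9.1.2 adds rules by toxicity. At grade 4, the diarrhea, rash, paronychia, hepatic, QTc, creatine kinase and ocular rows all end treatment (for example, "Discontinue study treatment"). Any other toxicity of grade 3 or above goes to the Other row. Its condition is "If Grade 3 or higher adverse reaction improves to grade ≤ 1 after withholding of osimertinib for up to 21 days" and its action is "Osimertinib may be restarted at the same dose (80 mg) or a lower dose (40 mg) at the discretion of the investigator". If the event does not improve in that time, osimertinib stops permanently.

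No section says whether 9.1.1 or Table 3 prevails where they differ.

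**The concern.** Two mandatory ladder items and one discretionary table row apply to the same patients. A site following item 5 takes a patient off treatment; a site following the Other row may restart that patient. Grade 4 is the sharper case, because the ladder omits it and the Other row is the only specific rule left for an unnamed grade 4 event.

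Cytopenias show that the gap concerns a recognised effect. Section 2.4 describes falls in platelets, neutrophils and leukocytes as known effects and sends investigators to Section 9 for interruption and reduction. Section 9 has no hematologic row, and blood counts are taken every cycle.

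The main stake is patient safety and consistent conduct across sites. There is a secondary link to the primary endpoint. Section 22.4.2 counts a patient who stops before confirmation as a non-responder. Scans are scheduled on day 1 of cycles 3 and 5, so on schedule the earliest confirmation is after four 28-day cycles, about week 16. A different stop or restart decision before then can change a patient's classification, and the final decision turns on 10 versus 11 confirmed responders among 37.

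**Working it through.** The plan states no figure on this point, so the check is a comparison of texts. Take a drug-related toxicity with no Table 3 row of its own, and compare the ladder's rule for grade 3 with the Other row's rule for grade 4.

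| Situation | Ladder, grade 3 | Other row, grade 4 | Comparison |
|---|---|---|---|
| First event at 80 mg, resolved within 21 days | 80 or 40 mg, discretion (item 3) | 80 or 40 mg, discretion | Same |
| Second event at 80 mg, resolved | Must reduce to 40 mg (item 4) | 80 or 40 mg, discretion | Grade 4 less restrictive |
| Event on 40 mg, resolved | Must discontinue (item 5) | Restart allowed; the wording equates the same dose with 80 mg, which does not fit this patient | Grade 4 less restrictive, or no clear rule |
| Not resolved in 21 days | Permanent stop (item 2) | Permanent stop | Same |

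The rules differ in two of the four situations. What the difference means depends on which text governs unnamed grade 3 events, since the Other row covers those as well:

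- If the ladder governs grade 3, the second and third rows of the table give grade 4 a less restrictive rule than grade 3.
- If the Other row governs grade 3 too, both grades get the same rule throughout, but items 4 and 5 are then contradicted for every unnamed toxicity.

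There is also an inconsistency within Table 3: grade 4 ends treatment in the seven named rows listed above, but not in the Other row.

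**Frequency.** The documents give no rate for second events, events on 40 mg, or unnamed grade 4 events. Section 2.4 gives AURA3 figures for osimertinib that allow a rough illustration:

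- Dose reduction for adverse events, 2.9%: 37 × 0.029 = 1.07 patients reaching 40 mg.
- Related grade 3 or higher events, 5.7%: 37 × 0.057 = 2.11 patients with a first such event.
- Assume the risk of a further grade 3 or higher event lies between 5.7% (related) and 22.6% (all causes).
- Event on 40 mg: 1.07 × 0.057 = 0.06 to 1.07 × 0.226 = 0.24 patients.
- Second event: 2.11 × 0.057 = 0.12 to 2.11 × 0.226 = 0.48 patients.

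These figures borrow rates from a different population and carry the overall rates over to patients who have already had an event. They omit ladder entry through intolerable grade 2 events, which makes them too low. They include named-row and unresolved events, which makes them too high. They indicate an order of magnitude only.

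**The case against.** The strongest reply is that the apparent inversion of severity comes from taking grade 3 from the ladder and grade 4 from the table. The Other row is written for grade 3 and above, and if it governs both, the grades are treated alike. This stands as a limit on the claim. It does not remove the defect, because that reading sets aside two mandatory ladder items.

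A second reply is that the Other row, by equating the same dose with 80 mg, assumes a patient taking 80 mg. A reader might infer that it permits a return to 80 mg after a grade 4 event on 40 mg. The wording does not clearly support that; it may simply be silent on such patients. In that case a grade 4 event on 40 mg that resolves has no specific rule, which still needs repair.

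Third, section 9.1.2 leaves other toxicities to institutional standards or discretion, and section 13.1 permits withdrawal for unacceptable toxicity. The first adds another rule without ranking it, and the second is permissive. Neither settles the conflict.

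Fourth, the cytopenia example should not be pressed. Section 2.4 says most patients had no change or a single grade change, reports no clinically significant sequelae, and gives no grade 4 rate.

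**Conclusion.** The contradiction is real but narrow. For unnamed toxicities that resolve within 21 days, ladder items 4 and 5 and the Other row give different instructions for a second event and for an event on 40 mg. Because items 1 to 5 omit grade 4, those two situations are handled less restrictively at grade 4 than at grade 3, provided the ladder governs grade 3.

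Two stronger readings are tempting and are not supported. One is that every unnamed grade 4 event gets a weaker rule than a grade 3 event; the rules agree for a first event and for an event unresolved at 21 days. The other is to size the problem by the chance of seeing any grade 4 event among 37 patients. That counts first events and named-row events, where this conflict does not arise, and the documents do not give the grade 4 share it would need.

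The conflicting situations are probably rare. Any effect on the response rate cannot be computed, and the stated Simon design figures are unaffected. The case for change rests on safety and consistent conduct. The dose schema figure was not available, but its title limits it to grade 3 and intolerable grade 2 events.

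**What to change.** Reconcile items 1 to 5 of section 9.1.1 with the Other row of Table 3. State where each of these is handled for toxicities without their own row: grade 4 events, second events, and events in patients already on 40 mg. State whether the Other row is meant to differ from the named rows at grade 4, and which text prevails wherever 9.1.1 and Table 3 differ. The content of each rule is for the clinical team.

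The cost is a wording amendment to one section and one table row, with the IRB approval that section 18.5 requires and notice to the Cancer Protocol Committee, since agent administration is affected. It needs no extra patients, visits or procedures. Depending on the rule chosen, investigators may have somewhat less discretion.
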